10.2 Secondary study parameter(s)

For the secondary continuous outcomes, the differences in scores for the DAA and PLA groups at the different times will be statistically tested using unpaired t-tests or its non-parametric equivalent based on whether the difference scores violate parametric assumptions or not. Categorical outcome parameters will be analyzed using Chi-square tests. If possible, 95% confidence intervals for the relevant estimates will be calculated.

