3. STUDY DESIGN

This study will be a single center, randomized controlled clinical trial (RCT). This study contains two arms, one with patients treated by means of the DAA and one with patients treated by means of the PLA.

Two surgeons will be participating in this study. Both are senior hip orthopedic surgeons for the NANOS prosthesis and both orthopedic surgeons will perform the DAA and the PLA. If the indication for primary hip arthroplasty is established, patients will be asked if they want to participate. Patients who are interested in participating will get an appointment with the research nurse after one week. Then informed consent will be signed and patients will be randomized to one of the two study arms. Registry of data and block randomization will be executed via Castor.

As primary outcome we will use the migration of the NANOS prosthesis in mm as measured with EBRA-FCA software. In addition, we will investigate functional outcome and quality of life with the HOOS and EQ-5D questionnaires.

Basic balance and gait performance will be tested using the timed “up & go” (TUG) test, instrumented with inertial sensors to measure body segment accelerations and angles, and a two times 50 meter walk at their preferred walking speed, also instrumented with inertial sensors⁸⁻¹². For the TUG test¹³, in short, participants will be asked to stand up from a chair, walk for 3 meters, walk back to the chair and sit down on the chair. The time needed to perform the TUG test as instructed will be registered. In addition, the participants will wear validated inertial sensors (McRoberts Dynaport Hybrid, Dimensions 87 x 45 x 14 mm, Weight 74 grams)¹⁴, which will be attached to the lower back with Velcro fixation.

The study will take place between 2017 and 2020 in the Noordwest Ziekenhuisgroep location Alkmaar.

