8.1.2 Secondary study parameters/endpoints

Secondary study parameters are the clinical, functional and surgical outcome parameters compared between the DAA and PLA:

- Perceived pain, measured using a Visual Analogue Scale (VAS) in the week before surgery, during hospitalization at days 1 to 3, at discharge, 8 weeks, three months, six months, one year after surgery and two years after surgery.
- Hip pain and symptoms assessed using the symptoms, pain and activities of daily living (ADL) subscales of the Hip Dysfunction and Osteoarthritis Outcome Score (HOOS) in the week before surgery, at 8 weeks, three months, six months, one year after surgery and two years after surgery.
- Hip range of motion in the week before surgery, at 8 weeks, three months, six months, one year after surgery and two years after surgery.
- Quality of life assessed using the EQ-5D in the week before surgery, at 8 weeks, three months, six months, one year after surgery and two years after surgery.
- Functioning during daily living assessed using the HOOS in the week before surgery, at 8 weeks, three months, six months, one year after surgery and two years after surgery.
- Hip abductor strength and gait quality before surgery, at 8 weeks and after 12 months.
- Length of hospital stay
- Operation time, blood loss, and other parameters of the surgical procedures
- All complications related to the surgery and rehabilitation
- Health status will be classified using the ASA score.
- Patient's pre-operative status, surgical procedure as well as clinical and radiological outcome will be documented.

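### Secondary scores measured before surgery are compared without baseline adjustment, which loses precision and leaves chance imbalance in a 56-patient trial

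*Protocol*

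**What the plan says.** Protocol 10.2 sets one method for every continuous secondary outcome: "the differences in scores for the DAA and PLA groups at the different times will be statistically tested using unpaired t-tests". A rank test is the fallback, and the choice between the two is made "based on whether the difference scores violate parametric assumptions or not". The section names no covariate and no repeated-measures model, and it does not define *difference scores*.

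Protocol 8.1.2 schedules a pre-operative value for each of the main scores:

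- Pain: "Perceived pain, measured using a Visual Analogue Scale (VAS) in the week before surgery".
- Quality of life: "Quality of life assessed using the EQ-5D in the week before surgery".
- Function: "Functioning during daily living assessed using the HOOS in the week before surgery". The HOOS pain and symptom subscales follow the same schedule.
- Range of motion: "Hip range of motion in the week before surgery".
- Abductor strength and gait quality: before surgery, at 8 weeks and at 12 months.

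Protocol 8.2 has baseline registered and then the patient randomised. Section 3 specifies block randomisation and names no stratification factor. Section 4.4 plans 56 patients.

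**The concern.** The objectives and hypotheses in section 2 include pain, function, range of motion, abductor force and gait, and these are judged by the tests in 10.2. A pre-operative measurement of the same quantity is usually among the best available predictors of the later value. If the analysis ignores it, two things follow. The standard error is larger than the collected data require, and any chance difference between the arms before surgery shows up partly as a difference after surgery. In a trial of this size, with no stratification named, such differences can be noticeable.

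10.2 chooses the test itself, so this is not a detail merely left to a statistical analysis plan.

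**Working it through.** **Inputs.** From Protocol 4.4: SD 0.31 mm, difference 0.25 mm, 80% power, two-sided 5%, 25 per group, 56 in total after the 10% allowance. Assumed: equal arms, and a baseline-outcome correlation rho of 0.3 to 0.7, because the Protocol gives none. The change-score column also assumes equal SDs at baseline and follow-up.

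**1. The plan's own figure.** n per arm = 2 × (1.960 + 0.842)² × 0.31² / 0.25² = 24.1, rounded up to 25. The exact t-test gives 25.1, with 79.8% power at 25. 50 / 0.90 = 55.6, so 56 in total, or 28 per arm. The stated size reproduces, and nothing below changes it.

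**2. Chance baseline imbalance.** The SE of the baseline difference, in SD units, is √(2/n) = √(2/28) = 0.27. The 95% range is ±1.96 × 0.267 = ±0.52 SD. The probability of a difference beyond 0.25 SD in either direction is 35%, and beyond 0.5 SD it is 6%.

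**3. How much of it carries over.** Given a baseline imbalance b, a follow-up-only comparison is shifted by rho × b. For b = 0.25 SD, that is 0.075, 0.125 or 0.175 SD at rho 0.3, 0.5 or 0.7. A change-score comparison is shifted the other way, by (1 − rho) × b: 0.175, 0.125 or 0.075 SD.

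**4. Precision.** Variances are relative to the follow-up-only t-test (1.00):

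- ANCOVA: (1 − rho²) × (1 + 1/(2n − 4)). The second factor is the small-sample cost of estimating the slope, 1 + 1/52 = 1.019 at n = 28.
- Change score: 2 × (1 − rho).

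| rho | ANCOVA | Cut against follow-up only | Change score | ANCOVA / change score |
|---|---|---|---|---|
| 0.3 | 0.91 × 1.019 = 0.93 | 7% | 1.40 | 66% |
| 0.5 | 0.75 × 1.019 = 0.76 | 24% | 1.00 | 76% |
| 0.7 | 0.51 × 1.019 = 0.52 | 48% | 0.60 | 87% |

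**5. In patients and detectable differences.** Dividing 28 by the ANCOVA variance, adjustment is worth about 30, 37 or 54 patients per arm. The difference detectable at 80% power is 0.76 SD unadjusted. With adjustment it is 0.76 × √(ANCOVA variance) = 0.73, 0.67 or 0.55 SD.

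**6. Sensitivity.** With 25 completers per arm the picture is almost the same: SE of imbalance 0.28 SD, and a detectable difference of 0.81 SD unadjusted against 0.71 SD at rho 0.5. If rho were zero, adjustment would cost about 2% in variance (1.019).

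**The case against.** The strongest reply is that 10.2 may already use the baseline. An unpaired t-test on change from baseline is a legitimate analysis, the words "based on whether the difference scores violate parametric assumptions or not" fit it, and the centre's pilot (Protocol 8.7) looked at differences between pre-surgery and one-year measurements. This stands as a reading, so it cannot be said as fact that the baseline goes unused. It does not remove the point, because the last column of the table shows ANCOVA with the smaller variance on that reading too.

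It is also true that the unadjusted tests keep their type I error and are unbiased on average under randomisation, that only secondary outcomes are involved, and that the gain is small if rho is near 0.3. All of this stands and limits the weight of the point.

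A reader might infer more than the Protocol supports:

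- **That a baseline imbalance passes whole into the result.** Only the fraction rho does, in a follow-up-only comparison.
- **That the baseline is taken after allocation is known.** Section 3 says "Then informed consent will be signed and patients will be randomized to one of the two study arms", 8.1.2 places questionnaires in the week before surgery, and patients are not blinded. But 8.2 registers baseline before randomising, and nowhere is the interval from consent to surgery given. A contradiction is not shown.
- **That the choice between t-test and rank test is made afresh at each visit.** 10.2 does not say so.
- **That patients with a missed questionnaire are handled wrongly.** 10.2 does not address this, and it is commonly left to an analysis plan.
- **That the number of secondary tests adds to the case.** Multiplicity is a separate question, and baseline adjustment does not address it.

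**Conclusion.** The point holds as one of efficiency, not validity. For secondary outcomes with a pre-operative value, 10.2 specifies a less precise comparison than the collected data allow, under either reading of its wording. The variance saving is about 7%, 24% or 48% against a follow-up-only test at rho 0.3, 0.5 or 0.7. Against a change-score test it is about 34%, 24% or 13% (100% minus 66%, 76% or 87%). These sizes rest on the assumed rho, which may well differ between outcomes and visits, and on 28 patients per arm. That adjustment gains precision does not depend on the exact value, unless rho is close to zero.

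The point does not extend to operation time, blood loss or length of stay, which have no baseline, or to the primary comparison of subsidence.

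**What to change.** In 10.2, for outcomes with a pre-operative value (VAS, HOOS, EQ-5D, range of motion, abductor strength, gait), replace the unpaired tests with one of the following:

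- ANCOVA at each visit, with approach and the baseline value as terms; or
- one mixed model per outcome with approach, time, approach-by-time and baseline.

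Report the adjusted DAA-PLA difference with its 95% CI at each visit. Keep the unadjusted tests for operation time, blood loss and length of stay. If *difference scores* remains anywhere in the section, define it.

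The cost is a change of wording in one section and slightly more analysis work. No new visits, measurements or patients are needed.

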10.3 Other study parameters

Not applicable

10.4 Interim analysis (if applicable)

Not applicable.

11. ETHICAL CONSIDERATIONS

11.1 Regulation statement

The study will be conducted according to the principles of the Declaration of Helsinki (2013), in accordance with the Good Clinical Practice guidelines of the International Conference on Harmonisation and in accordance with the Medical Research Involving Human Subjects Act (WMO).

11.2 Recruitment and consent

Subjects shall be informed using a study patient information document at least five days before the procedure to ensure an informed decision for consent and inclusion. Inclusion shall be done by competent orthopaedic surgeons, residents or nurse practitioners / physician assistants who will be trained in informing about the study in a research meeting. Signing of informed consent has to be done prior to any study related activities.

11.3 Objection by minors or incapacitated subjects (if applicable)

Not applicable

11.4 Benefits and risks assessment, group relatedness

This study might provide evidence for a device which will improve clinical, functional and surgical outcome after total hip arthroplasty for younger and active patients in need of total hip arthroplasty in the future and at low risk and no extra cost for patients in this study.

11.5 Compensation for injury

Previous use of the NANOS stem has been previously done in a prospective trial and has not led to a higher complication rate than we see after regular THA. All patients will undergo the normal follow-up protocol and will attend one additional follow up visit. Since total hip placement procedures are common practice in the Noordwest Ziekenhuisgroep Alkmaar and the Nanos had been previously used by the collaborating surgeons. We do not suspect additional complications.

Although short to midterm results with the NANOS stem are favorable, there is no documented long term follow-up. Therefore, the investigator has a liability insurance for the 58 patients that will undergo Nanos placement which is in accordance with article 7, subsection 9 of the WMO.

The sponsor (also) has an insurance which is in accordance with the legal requirements in the Netherlands (Article 7 WMO and the Measure regarding Compulsory Insurance for

Clinical Research in Humans of 23th June 2003). This insurance provides cover for damage to research subjects through injury or death caused by the study.

1. € 650.000,-- (i.e. six hundred and fifty thousand Euros) for death or injury for each subject who participates in the Research;
2. € 5.000.000,-- (i.e. five million Euro) for death or injury for all subjects who participate in the Research;
3. € 7.500.000,-- (i.e. seven million five hundred thousand Euros) for the total damage incurred by the organisation for all damage disclosed by scientific research for the Sponsor as 'verrichter' in the meaning of said Act in each year of insurance coverage.

The insurance applies to the damage that becomes apparent during the study or within 4 years after the end of the study.

11.6 Incentives (if applicable)

Not applicable

12. ADMINISTRATIVE ASPECTS, MONITORING AND PUBLICATION

12.1 Handling and storage of data and documents

All data will be handled confidentially by the investigator. Each subject will receive an identification code; this code will be used to link the data to the subject. The key to the code will be safeguarded by the investigator. Data will be kept for fifteen years.

12.2 Monitoring and Quality Assurance

Monitoring of the study will be conducted by a qualified GCP-proof monitor.

12.3 Amendments

Amendments are changes made to the research after a favorable opinion by the accredited METC has been given. All amendments will be notified to the METC that gave a favorable opinion.

12.4 Annual progress report

The sponsor/investigator will submit a summary of the progress of the trial to the accredited METC once a year. Information will be provided on the date of inclusion of the first subject, numbers of subjects included and numbers of subjects that have completed the trial, serious adverse events/ serious adverse reactions, other problems, and amendments.

12.5 End of study report

The investigator will notify the accredited METC of the end of the study within a period of 8 weeks. The end of the study is defined as the final patient's last study visit.

In case the study is ended prematurely, the investigator will notify the accredited METC within 15 days, including the reasons for the premature termination.

Within one year after the end of the study, the investigator/sponsor will submit a final study report with the results of the study, including any publications/abstracts of the study, to the accredited METC.

12.6 Public disclosure and publication policy

No arrangements made between the sponsor and the investigator concerning the public disclosure and publication of the research data. Data will be published in a(n) (inter)national scientific journal. The CCMO statement on publication policy will be followed.

13. STRUCTURED RISK ANALYSIS

Not applicable

13.1 Potential issues of concern

Not applicable

13.2 Synthesis

Not applicable

